Appendix 5-Table 1 Highly Effective Contraceptive Methods

Highly Effective Contraceptive Methods That Are User-Dependent^a

(Failure rate of < 1% per year when used consistently and correctly)

- Combined (estrogen- and progestogen-containing) hormonal contraception associated with inhibition of ovulation:
 - o Oral
 - Intravaginal
 - Transdermal
- Progestogen-only hormonal contraception associated with inhibition of ovulation:
 - o Oral
 - Injectable

Highly Effective Methods That Are User-Independent

(Failure rate of < 1% per year)

- Implantable progestogen-only hormonal contraception associated with inhibition of ovulation^a
- Intrauterine device (IUD)
- Intrauterine hormone-releasing system (IUS)
- Bilateral tubal occlusion

Vasectomized partner

A vasectomized partner is a highly effective contraception method provided that the partner is the sole male sexual partner of the WOCBP and the absence of sperm has been confirmed. If not, an additional highly effective method of contraception should be used.

Sexual abstinence

Sexual abstinence is considered a highly effective method only if defined as refraining from heterosexual intercourse during the entire period of risk associated with the study treatment. The reliability of sexual abstinence needs to be evaluated in relation to the duration of the study and the preferred and usual lifestyle of the participant.

Appendix 5-Table 1 Highly Effective Contraceptive Methods (cont.)

Acceptable Birth Control Methods Which May Not Be Considered As Highly Effective (Failure rate of > 1% per year when used consistently and correctly)

- Progestogen-only oral hormonal contraception, where inhibition of ovulation is not the primary mode of action
- Male or female condom with or without spermicide b
- Cap, diaphragm or sponge with spermicide ^b
- Hormonal contraception may be susceptible to interaction with the IMP, which may reduce the efficacy of the contraception method.
 - Typical use failure rates may differ from those when used consistently and correctly. Use should be consistent with local regulations regarding the use of contraceptive methods for participants participating in clinical studies.
- b) A combination of male condom with either cap, diaphragm or sponge with spermicide (double barrier methods) are also considered acceptable, but not highly effective, birth control methods. i.e., when the risk of teratogenicity and genotoxicity is unlikely.

3. **PREGNANCY TESTING**

For WOCBP enrolled in the study, blood sample and urine pregnancy tests will be performed according to respective treatment arm specific Schedule of Activities table. If a urine pregnancy test is positive, it must be confirmed by a blood pregnancy test.

Pregnancy testing will be performed whenever a menstrual cycle is missed or when pregnancy is otherwise suspected and according to local practice.

4. COLLECTION OF PREGNANCY INFORMATION

Male participants with partners who become pregnant

The Investigator will attempt to collect pregnancy information on any male participant's female partner who becomes pregnant while the male participant is in this study (see Section 8.3.5 Pregnancy).

Attempts should be made to collect and report details of the course and outcome of any pregnancy in the partner of a male participant exposed to study treatment. The Investigator will record pregnancy information on the Clinical Trial Pregnancy Reporting Form and submit it to the Sponsor within 24 hours of learning of the partner's pregnancy. When permitted by the site, the pregnant partner would need to sign an Authorization for Use and Disclosure of Pregnancy Health Information to allow for follow-up on her pregnancy. If the authorization has been signed, the Investigator should update the Clinical Trial Pregnancy Reporting Form with additional information on the course and outcome of the pregnancy when available. An Investigator who is contacted by the male participant or his pregnant partner may provide information on the risks of the pregnancy and the possible effects on the fetus, to support an informed decision in cooperation with the treating physician and/or obstetrician. The female partner will be followed to determine the outcome of the pregnancy. Information on the status of the mother and

child will be forwarded to the Sponsor. Monitoring of the participant's partner should continue until conclusion of the pregnancy. Any termination of the pregnancy will be reported regardless of fetal status (presence or absence of anomalies) or indication for procedure.

Female participants who become pregnant

The Investigator will collect pregnancy information on any female participant, who becomes pregnant while participating in this study (see Section 8.3.5 Pregnancy). Information will be recorded on the appropriate form and submitted to the Sponsor within 24 hours of learning of a participant's pregnancy. The participant will be followed to determine the outcome of the pregnancy. The Investigator will collect follow-up information on the participant and the neonate, which will be forwarded to the Sponsor. Monitoring of the participant should continue until conclusion of the pregnancy. Any termination of pregnancy will be reported, regardless of fetal status (presence or absence of anomalies) or indication for procedure.

While pregnancy itself is not considered to be an AE or SAE, and should not be recorded on the AE eCRF, any pregnancy complication will be reported as an AE or SAE. A spontaneous abortion is always considered to be an SAE and will be reported as such. Any post-study pregnancy related SAE considered reasonably related to the study treatment by the Investigator, will be reported to the Sponsor as described in Appendix 2. While the Investigator is not obligated to actively seek this information in former study participants, he/she may learn of an SAE through spontaneous reporting.

Any female participant who becomes pregnant while participating in the study will discontinue study treatment.

5 ABORTIONS

Any spontaneous abortion should be classified as a serious adverse event (as the Sponsor considers spontaneous abortions to be medically significant events), recorded on the Adverse Event eCRF, and reported to the Sponsor immediately (i.e., no more than 24 hours after learning of the event; see Appendix 2, Section 5).

Any induced abortion due to maternal toxicity and/or embryofetal toxicity should also be classified as serious adverse event, recorded on the Adverse Event eCRF, and reported to the Sponsor immediately (i.e., no more than 24 hours after learning of the event; see Appendix 2, Section 5).

Elective or therapeutic abortion not associated with an underlying maternal or embryofetal toxicity (e.g., induced abortion for personal reasons) does not require expedited reporting but should be reported as outcome of pregnancy on the Clinical Trial Pregnancy Reporting Form.

6 CONGENITAL ANOMALIES/BIRTH DEFECTS

Any congenital anomaly/birth defect in a child born to a female participant, or female partner of a male participant exposed to study treatment, should be classified as a serious adverse event, recorded on the Adverse Event eCRF, and reported to the Sponsor immediately (i.e., no more than 24 hours after learning of the event).

Appendix 6 Planned, Ongoing, and Terminated Treatment Arms And Terminated Arm Safety Follow Up

An overview of the planned, ongoing, and terminated treatment arms is shown in Appendix 6-Table 1.

Arms depicted in Appendix 6-Table 1 as 2 and 6, were terminated due to Sponsor's decision to discontinue the development of CpAM (RO7049389) in the NUC-suppressed CHB participant population. At the time this decision was taken the CpAM+TLR7+NUC arm was fully recruited and the siRNA+CpAM+NUC arm was partially recruited. As a result of this decision, no further participants were enrolled in the siRNA+CpAM+NUC arm and the participants who were already randomized to both treatment arms were asked to attend an early termination visit to discontinue both study drugs, maintain NUC therapy, and enter the safety follow-up period.

Appendix 6-Table 1 Planned, Ongoing, and Terminated Treatment Arms

Arm	Treatment Arm	Arm Status	Number of Participants	Link to Appendix
1	NUC control	Ongoing	30 ^b	Appendix 7
2	CpAM (600 mg) (RO7049389) + TLR7 (150 mg) (RO7020531) + NUC	Terminated ^c	~30	Appendix 8
3	siRNA (100 mg) (RO7445482) + NUC	Ongoing	~30	Appendix 9
4	siRNA (200 mg) (RO7445482) + NUC	Ongoing	~30	Appendix 9
5	siRNA (200 mg) (RO7445482) + PEG-IFN (180 μg)+ NUC	Ongoing	~30	Appendix 10
6	siRNA (200 mg) (RO7445482) + CpAM (600 mg) (RO7049389) + NUC	Terminated ^c	~30	Appendix 11
7	siRNA (200 mg) (RO7445482) + TLR7 (150 mg) (RO7020531) + NUC	Ongoing	~30	Appendix 12
8	siRNA (200 mg) (RO7445482) + PD-L1 LNA (RO7191863) + NUC – 24 week treatment	Planned	~30	Appendix 13
9	siRNA (200 mg) (RO7445482) + PD-L1 LNA (RO7191863) + NUC – 36 week treatment	Planned	~30	Appendix 13
TBDa	TBD		TBD	TBD

Abbreviations: NUC=nucleos(t)ide; TBD=to be determined.

^a Additional treatment arms may be added to the study.

^b Additional participants will be added as additional treatment arms are added to the study.

^c Treatment arms terminated; patients performed early termination visit and entered in the safety follow-up period.

Appendix 6-Table 2 Mechanism of Action Classification for Investigational Medicinal Products

IMP	Target	Mechanism of Action
CpAM (RO7049389)	HBV core protein	DAA: Core protein allosteric modulator (class I)
TLR7 (RO7020531)	Human toll-like receptor 7	IM: Toll-like receptor 7 agonist
siRNA (RO7445482)	HBV RNA transcripts	DAA: HBV gene expression inhibitor
PD-L1 LNA (RO7191863)	PD-1/PD-L1 checkpoint inhibitory pathway	IM: PD-L1 inhibitor

Appendix 6-Table 3 Applicable Inclusion/Exclusion Criteria

Treatment arm	Applicable Exclusion Criteria		
NUC Control Arm	Section 5.2		
CpAM (RO7049389) + TLR7 (RO7020531) + NUC	Section 5.2 and Section A8.4 in Appendix 8		
siRNA (100 mg) (RO7445482) + NUC	Section 5.2 and Section A9.4 in Appendix 9		
siRNA (200 mg) (RO7445482) + NUC	Section 5.2 and Section A9.4 in Appendix 9		
siRNA + PEG-IFN + NUC	Section 5.2 and Section A10.4 in Appendix 10		
siRNA (RO7445482) + CpAM (RO7049389) + NUC	Section 5.2 and Section A11.4 in Appendix 11		
siRNA (RO7445482) + TLR7 (RO7020531) + NUC	Section 5.2 and Section A12.4 in Appendix 12		
siRNA (RO7445482) + PD-L1 LNA (RO7191863) + NUC	Section 5.2 and Section A13.4 in Appendix 13		

SAFETY FOLLOW UP FOR PARTICIPANTS FROM EARLY TERMINATED STUDY TREATMENT ARM BY THE SPONSOR

Participants, who permanently discontinue study treatment as part of an early termination of a treatment arm due to Sponsor's decision, will undergo safety follow-up assessments as described in Appendix 6-Table 4 and participants will remain on their NUC therapy.

All participants will be followed up for 24 weeks according to the following Schedule of Assessments.

Appendix 6-Table 4 Schedule of Activities of Safety Follow-up Period for Early Terminated Study Treatment Arms

			Follow-u	p Period ^a	
	Week	4	8	12	24
	Day	28 (±3)	56 (±3)	84 (±7)	168 (±7)
Physical examination, vital signs ^{b, c}					Х
ECG					Х
Abdominal ultrasound					Х
Alfa-fetoprotein					Х
Pregnancy test ^d		Х	Х	х	Х
Thyroid function tests					Х
Hematology		Х	Х	х	Х
Chemistry		х	x	х	Х
Coagulation		Х	х	х	Х
GLDH		Х	Х	х	Х
Urinalysis		Х	х	х	Х
HBV serology (HBsAg, HBeAg, anti-HBs, anti-HBe)		х	Х	х	х
HBV DNA quantitative		Х	Х	х	Х
HBV RNA quantitative		х	х	х	Х
NME ADA ^e				х	Х
Diary review		х	Х	х	Х
Adverse events & concomitant medications		х	Х	х	х

DNA = deoxyribonucleic acid; ECG = electrocardiogram; GLDH = glutamate dehydrogenase; HBeAg = hepatitis B e antigen; HBsAg = hepatitis B surface antigen; RNA = ribonucleic acid.

Note, for participants who are in treatment arms NOT terminated by the sponsor, the above safety follow-up is not applicable. The follow up period for these patients is as per the SoA of the respective treatment arm.

^a Safety follow-up is mandatory for 24 weeks for all participants. Additional unscheduled visits may be performed if deemed clinically relevant.

^b Limited symptom-directed physical exam and as clinically indicated.

^c Blood pressure, pulse rate, respiratory rate and body temperature obtained at least 5 minutes after participant has been in supine/sitting position.

^d Pregnancy testing for females of childbearing potential only to be conducted monthly at the visit or at home using pregnancy kits supplied by sponsor or obtained locally; If urine test is positive, it must be confirmed by a serum test.

^e As applicable according to impacted study arm.

Appendix 7 Study Details Specific to NUC Control Arm

[figure not shown]
An overview of the nucleos(t)ide (NUC) control treatment arm is shown in Appendix 7-Figure 1.

Participants will continue their background NUC therapy for the 48-week treatment period. At the end of the treatment period, in line with current CHB treatment guidelines, participants will continue NUC treatment during the follow-up unless the NUC discontinuation criteria have been met (see Section 6.8).

Initially, 30 participants will be randomized to the NUC control arm. The subsequent randomization ratio will depend on the number of actively enrolling NME treatment arms, with the stipulation that no more than 17% of participants will be randomly allocated to the NUC control arm.

Participants in the NUC control arm who complete the follow-up Week 48 visit, and continue to meet the study eligibility criteria, may be offered to participate in an expansion cohort of a combination regimen within this study. This will allow access for NUC control participants to an investigational combination regimen that has shown a positive benefit/risk profile, as this is a pre-requisite for an expansion cohort to commence.

Appendix 7-Figure 1 NUC Control Treatment Arm

A7.1 BACKGROUND SPECIFIC TO NUC CONTROL ARM

Not applicable.

A7.2 BENEFIT/RISK ASSESSMENT SPECIFIC TO NUC CONTROL ARM

Although participants randomized to the control arm are not expected to receive additional benefit within this arm beyond that attained with their current treatment, the control arm is important to increase the robustness of the study in terms of the clinical data generated, and in identifying efficacious combination regimens. In turn, their participation will guide further clinical development and thereby benefit the overall CHB population.

Furthermore, after completing the follow-up Week 48 visit, participants who meet the study eligibility criteria may be offered to participate in an expansion cohort of a combination regimen within this study. The expansion cohort may result in additional therapeutic benefit for the participants.

A7.3 JUSTIFICATION FOR DOSE SPECIFIC TO NUC CONTROL ARM Not applicable.

A7.4 LIFESTYLE CONSIDERATIONS SPECIFIC TO NUC CONTROL ARM

NUCs will be given according to the local prescribing information.

A7.5 TREATMENT ADMINISTERED SPECIFIC TO NUC CONTROL ARM

Appendix 7-Table 1 summarizes the treatments administered.

Appendix 7-Table 1 Summary of Treatments Administered for NUC Control Treatment Arm

Study Treatment Name	NUC
IMP and NIMP	NIMP*
Dose Formulation	Film-coated tablet
Unit Dose Strength(s)/Dosage Level(s)	Refer to local prescription information
Dose	ETV: 0.5 mg TDF: 300 mg TAF: 25 mg
Route of Administration	oral
Sourcing	Provided centrally by the Sponsor or locally by the study site
Packaging and Labeling	Study treatment will be packaged and labeled as required per local regulation.

^{*}NUC are considered IMP in the UK only.

For guidelines for dosage modification, please refer to the NUC local prescribing information.

For more details, refer to the NUC local prescribing information and the Pharmacy Manual.

A7.6 PHARMACODYNAMICS AND BIOMARKERS ANALYSES SPECIFIC TO NUC CONTROL ARM

A7.6.1 CLINICAL GENOTYPING

If safety or activity rationales develop, clinical genotyping will be performed (see Sections 8.7.4.1 and 8.8.1.1). Known candidate genes of interest that are stated in appendices for NME combination arms will be queried in the NUC control arm as well.

A7.7 SCHEDULE OF ACTIVITIES (NUC CONTROL ARM)

An overview of the schedule of the activities is provided in Appendix 7-Table 2.

Appendix 7-Table 2 Schedule of Activities for NUC Control Arm

	Scree	Screening Treatment Period											Foll	ow-up	Period					VB/VR	UV(Flu like/ ET) ^p
Week			1	4	12	24	36	48 ⁿ	2 °	4°	6 °	8 °	10 °	12	16 ⁰	20 °	24 q	36	48		-
Day	-56 to -7	-14 to -7	1	28 (± 3)	84 (± 3)	168 (± 7)	252 (± 7)	336 (± 7)	14 (±3)	28 (±3)	42 (±3)	56 (±3)	70 (±3)	84 (±7)	112 (±7)	140 (±7)	168 (±7)	252 (±7)	336 (±7)		
Informed consent	х																				
Demography, medical history	х																				
Physical examination, vital signs ^{a, b}	х		х	х	х	х	х	х									х		x	х	х
Randomization			Х																		
ECG	Х		Х		Х	Х	Х	х									Х		х		
Transient elastography/ARFI/MR ^c	х																				
Abdominal ultrasound	х					х		х									х		х		
Alfa-fetoprotein	х					х		х									х		Х		
HAV, HCV, HDV, HEV, HIV	х																				
Autoantibodies ^d	х																				
Alcohol and drugs of abuse screen ^e		х						х													х
Pregnancy test ^f		х			х	х	х	х						х			х	х	х		
Thyroid function tests	х				х	х		х									х		х		
Hematology (include HbA1c ^g)	х		х		х	х		х	х	х	х	х	х	х	х	х	х	х	х	х	х
Chemistry		х	х		х	х		х	х	х	х	х	х	х	х	х	х	х	х	x	х
Coagulation	х		Х		х	х		х	х	х	х	х	х	х	х	х	Х	х	х	x	х
GLDH	х		Х		х	х		х	х	х	х	х	х	х	х	х	х	х	х	x	х
Urinalysis	х		х		х	Х		х	х	х	х	Х	х	х	х	х	х	х	х	x	х

Appendix 7-Table 2 Schedule of Activities for NUC Control Arm (cont.)

	Scree	Screening Treatment Period											Foll	low-up	Period					VB/VR	UV(Flu like/ ET) ^p
Week			1	4	12	24	36	48 ⁿ	2 °	4 °	6 °	8 °	10 °	12	16 ⁰	20 °	24 ^q	36	48		-
Day	-56 to -7	-14 to -7	1	28 (± 3)	84 (± 3)	168 (± 7)	252 (± 7)	336 (± 7)	14 (±3)	28 (±3)	42 (±3)	56 (±3)	70 (±3)	84 (±7)	112 (±7)	140 (±7)	168 (±7)	252 (±7)	336 (±7)		
Clinical genotyping h			Х																		
HBV serology (HBsAg, HBeAg, anti-HBs, anti-HBe)	х		х	х	х	x	х	х	х	х	х	х	х	х	x	x	x	х	х	x	х
HBV DNA quantitative ^r	х		Х	х	х	х	х	х	х	х	х	х	х	х	х	х	х	Х	Х	х	х
Total HBsAg ⁱ			х	х	х	х	х	х		х		х		х			х		х	х	
HBcrAg			х	х	х	х	х	х		х		х		х			х		х	х	
Total anti-HBc quantitative			Х		х	х	х	х						х			х		х		
HBV RNA quantitative			х	х	х	х	х	х		х		х		х			х		Х	х	
HBV RNA sequencing h			х																		
HBV DNA sequencing ^j																				х	
Plasma PK (NUC) k			х		х	х	х	х												x	
RBR ^I			Х			х	х	х												х	
Study treatment administration &/or diary review			х	х	х	х	х	х	х	х	х	х	х	х	х	х	х	х	x	х	х
Adverse events & concomitant medications ^m			х	х	х	х	х	х	х	х	х	х	х	х	х	х	х	х	х	х	х

ARFI = acoustic radiation force impulse; DNA = deoxyribonucleic acid; ECG = electrocardiogram; ET= early termination; GLDH = glutamate dehydrogenase; HAV/HBV/HCV/HDV/HEV = hepatitis A/B/C/D/E virus; HBcrAg = hepatitis B core-related antigen; HBeAg = hepatitis B e antigen; HBsAg = hepatitis B surface antigen; HIV = human immunodeficiency virus; MR = magnetic resonance; NUC = nucleos(t)ide analogue; PK = pharmacokinetics; RBR = Research Biosample Repository; RNA = ribonucleic acid; Total HBsAg = post-dissociation of HBsAg/HBsAb complexes/components of HBsAg; VB/VR = virological breakthrough/relapse; UV= unscheduled visit.

^a Full physical exam at screening and Week 48. Limited symptom-directed physical exam at other visits and as clinically indicated. Height at screening only. Weight at screening, Day 1, and Week 12, 24, 36, 48.

Appendix 7-Table 2 Schedule of Activities for NUC Control Arm (cont.)

- ^b Blood pressure, pulse rate, respiratory rate and body temperature obtained at least 5 minutes after participant has been in supine/sitting position.
- ^c Historical liver biopsy or transient elastography/ARFI/MR/2D- shear wave elastography [2D-SWE] results obtained within 6 months prior to randomization are also acceptable. During screening transient elastography/ARFI/MR/2D-SWE are acceptable.
- ^d Autoantibodies refer to ANA, AMA, ASMA, and a-TPO.
- ^e Alcohol and drugs of abuse screen to be conducted according to local procedures.
- f Pregnancy testing for females of childbearing potential only; serum test at screening, urine test at other visits. If urine pregnancy test is positive, the pregnancy must be confirmed by a serum test.
- g HbA1c should be assessed only at screening.
- h If not collected at Day 1, samples for clinical genotyping and HBV RNA sequencing can be collected at any subsequent time point. The sample for HBV RNA sequencing aims at determining the HBV genotype. The HBV genotype may also be inferred using alternative approaches, such as serovariant determination.
- ⁱ Total HBsAg refers to HBsAg measured post-dissociation of HBsAg/HBsAb complexes/components of HBsAg.
- ightharpoonup HBV DNA sequencing will be collected in case of virological breakthrough/relapse, blood sample to be collected up to 6 times.
- ^k Plasma PK samples for NUC to be collected at pre-dose. During the PK assessments for VB/VR visits, only one predose sample is required for collection, no other additional time points should be collected.
- ¹RBR samples collected only from RBR-consenting participants.
- ^m Pre-treatment, only serious adverse events should be reported.
- ⁿ Participants who achieve HBsAg loss during treatment or during follow-up will discontinue NUC.
- o Additional post-treatment visits for participants who discontinued NUC at Week 48. If participants discontinue NUC later in the follow-up additional visits *should* be scheduled with a frequency of every 2 weeks for the first three months and every 4 weeks up to week 48 of follow-up period.
- ^p Participants who permanently discontinue study treatment will need to attend an unscheduled/early termination visit.
- ^q Visit window may be extended to +6 weeks in extreme circumstances such as pandemic, natural disasters, supply chain disruption, outbreak of hostilities.
- r Participants with HBV DNA > 2,000 IU/mL during the follow-up period will undergo weekly monitoring. Participants with HBV DNA > 20 IU/mL but < 2,000 IU/mL, should undergo monitoring every two weeks. Participants, who have discontinued NUC therapy at EOT, should have monthly visits from follow-up Week 24 to Week 48, instead of the 3 monthly follow-up visits shown in SoA, to enable early detection and appropriate management of HBV DNA rebound. At these additional unscheduled monitoring visits, the following laboratory assessments should be performed using the unscheduled lab kit: hematology, chemistry, coagulation, GLDH, urinalysis, HBV serology, HBV DNA quantitative, total HBsAg, HBcrAg, and HBV RNA quantitative.

Note: Additional assessments may be conducted before randomization if required by other arms that are currently recruiting as described in Section 5.2.

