5. STUDY POPULATION

The study population rationale is provided in Section 4.2.1.

The study will enroll CHB participants with preserved liver function and without significant fibrosis/cirrhosis.

The initial study population will consist of virologically suppressed CHB participants on NUC therapy between 18 and 65 years of age, inclusive, who fulfil all of the study eligibility criteria. Additional participant populations (e.g., treatment naïve CHB participants) may be explored within the study in treatment arms to be added at a later date pending new submission and HA/EC approval.

Prospective approval of protocol deviations from eligibility inclusion/exclusion criteria, also known as protocol waivers or exemptions are not permitted.

Any treatment arm-specific inclusion/exclusion criteria defined in the corresponding appendix (of actively recruiting arms), takes precedence over the inclusion/exclusion criteria defined in Section 5.1 and Section 5.2.

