6.8 CRITERIA FOR STOPPING NUCLEOSIDE ANALOGUE

Participants who complete the treatment period will stop NUC *therapy* if laboratory results on samples taken at end-of-treatment or at any of the follow-up visits show:

- ALT<1.25× baseline values, AND
- HBV DNA<LLOQ or<20 IU/mL, AND
- negative HBeAg, AND
- HBsAg <100 IU/mL and $\geq 1 \log_{10} IU/mL$ decline from baseline or HBsAg loss.

These criteria for stopping NUCs do not apply to any patients who have discontinued study drug prematurely for any reason.

7. DISCONTINUATION OF STUDY TREATMENT, PARTICIPANT DISCONTINUATION/WITHDRAWAL FROM THE STUDY AND LOST TO FOLLOW-UP

Participants have the right to voluntarily discontinue study treatment or withdraw from the study at any time for any reason.

An excessive rate of withdrawals (either participants discontinuing study treatment or withdrawing from the study) can render the study non-interpretable. Therefore, unnecessary withdrawal of participants should be avoided and efforts should be taken to motivate participants to comply with all the study-specific procedures as outlined in this protocol.

Details on study and site closures are provided in Appendix 1.

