8.3.8.2 Management of Virological Relapse

Participants who have discontinued all study treatments (NME combinations) including NUC therapy should be followed up every 2 weeks for first 12 weeks, thereafter monthly up to week 48 of the follow up period to enable early detection of HBV DNA rebound and appropriate management of virological relapse.

In addition, participants with HBV DNA > 20 IU/mL but < 2,000 IU/mL in follow-up, should undergo monitoring every two weeks.

Participants who discontinue all study treatment (NME combination and NUC therapy for the treatment arms or NUC therapy for the NUC control arm) and subsequently experience virological relapse (HBV DNA > 2,000 IU/mL) during the follow-up period will undergo weekly monitoring: an unscheduled blood sample will be collected for potential HBV genome characterization and where feasible phenotyping.

NUC therapy *should* be restarted in the following scenarios:

- *HBV DNA* > 20,000 *IU/mL* (regardless of other biochemical parameters or ALT values)
- HBV DNA > 2,000 IU/mL and ALT > 1.5 x ULN
- HBV DNA > 2,000 IU/mL and ALT ≤ 1.5 x ULN and if the retest (central or local laboratory) of HBV DNA performed within 1 week after availability of the initial results from the central laboratory confirms HBV DNA > 2,000 IU/mL (regardless of ALT values or other biochemical parameters)
- Immediately restart treatment in participants with clinically significant signs of decreasing liver function based on laboratory findings (e.g., INR, direct bilirubin) or clinical assessments (e.g., ascites, hepatic encephalopathy) regardless of HBV DNA or ALT levels.

For these additional unscheduled monitoring visits, the following laboratory assessments should be performed using the unscheduled lab kit: hematology, chemistry, coagulation, GLDH, urinalysis, HBV serology, HBV DNA quantitative, Total HBsAg, HBcrAg, and HBV RNA quantitative.

Note: The guidance for the management of virological relapse (frequency of monitoring, laboratory assessments, NUC restarting rules) described in this section should be followed in conjunction with the guidance for the management of elevated ALT levels described in Section 8.3.8.3.

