4.2.3 Sensitivity Analyses

- A) Following sensitivity analyses for the primary endpoint will be carried out to assess the impact of consecutive missing doses of siRNA
 - Completer Analyses (only include participants who have had full siRNA dosing)
 - All patients (mITT population including 'unevaluable' patients)
- B) Sensitivity analysis will be performed on primary endpoint for the patients who achieve HBsAg loss at the primary endpoint but did not meet the NUC stopping criteria. A non-responder imputation will be implemented for these pts.
- C) Sensitivity analysis may be performed using stratification based on IxRS data if higher number of inconsistencies are observed compare to the actual stratification.

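### Footnote n of the NUC control schedule stops NUC on HBsAg loss alone, which conflicts with the four joint conditions in Section 6.8 that the Appendix 7 text applies

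*Protocol*

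**What the plan says.** Protocol Section 6.8 governs stopping of NUC. It covers participants who complete the treatment period and applies when "laboratory results on samples taken at end-of-treatment or at any of the follow-up visits show" that all of its conditions are met. The first is "ALT<1.25× baseline values, AND"; the second is HBV DNA below the LLOQ or 20 IU/mL; the third is a negative HBeAg. The fourth concerns HBsAg and can be met in two ways: a level under 100 IU/mL with at least a 1 log10 "decline from baseline or HBsAg loss". The section adds that the criteria do not apply to anyone who stopped study drug early.

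The text of Appendix 7 keeps control participants on NUC for the 48-week treatment period. After that, "participants will continue NUC treatment during the follow-up unless the NUC discontinuation criteria have been met (see Section 6.8").

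Footnote n of Appendix 7-Table 2, whose marker sits on the Week 48 column, reads: "Participants who achieve HBsAg loss during treatment or during follow-up will discontinue NUC".

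SAP Section 4.2.3, item B, plans a non-responder imputation for "patients who achieve HBsAg loss at the primary endpoint but did not meet the NUC stopping criteria".

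Protocol Section 8.3.8.2 sets out off-NUC monitoring and restart rules, and it names those stopping "NUC therapy for the treatment arms or NUC therapy for the NUC control arm".

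**The concern.** Two current protocol texts give different instructions on when to withdraw antiviral therapy in the control arm. The footnote is directive and names HBsAg loss as the only trigger. Section 6.8 treats HBsAg loss as one way of meeting the last of four joint conditions. A site working from the schedule could stop NUC in someone whom Section 6.8 keeps on it.

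Entry criteria do not rule this out. They require suppressed HBV DNA and ALT of at most 1.5 x ULN, but the Section 6.8 ALT test is relative to the participant's own baseline. A participant whose ALT is normal throughout can therefore fail it.

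What is at stake is the care of very few control participants and consistent conduct between arms. The schedules in Appendices 9, 10, 12 and 13 carry no such footnote, so read literally only the control arm has this rule.

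**Working it through.** **Comparing the two rules**

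| Feature | Section 6.8 (applied by the Appendix 7 text) | Footnote n |
|---|---|---|
| Who | Completers of the treatment period | Anyone with HBsAg loss |
| When | End-of-treatment or follow-up samples | During treatment or follow-up |
| ALT, HBV DNA, HBeAg | All three required | Not mentioned |
| HBsAg | Below 100 IU/mL with at least 1 log10 decline, or loss | Loss only |

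The rules differ in every row. The row that matters for care is the third.

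*Is HBsAg loss a stand-alone route in Section 6.8?* No. The phrase sits inside the fourth bullet, and each earlier bullet ends with AND. SAP item B agrees: if HBsAg loss alone met the criteria, a completer with loss could not have failed to meet them.

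*Does the appendix override the body?* The only precedence rule of this kind is in Protocol Section 5. It says that arm-specific eligibility criteria in an appendix "takes precedence over the inclusion/exclusion criteria defined in Section 5.1 and Section 5.2". It does not reach stopping rules, and here the appendix text itself points to Section 6.8.

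**Size**

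The plan gives no figure for this point, so there is none to reproduce. Inputs:
- Control response rate 3% at 24 weeks post-EOT (Protocol Section 9.2).
- Initial control arm of 30 (Appendix 7).
- ALT threshold 1.25 x baseline (Section 6.8).
- Within-person ALT CV c of 10%, 20% or 30%. This is an assumption; the documents give no ALT variability.

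Step 1. Expected controls with HBsAg loss at 24 weeks post-EOT: 0.03 x 30 = 0.9.

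Step 2. Probability q of failing the ALT condition at one visit by within-person variation alone. Take baseline and follow-up ALT as independent lognormal values around one stable personal level:

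sigma = sqrt(ln(1 + c^2)); q = 1 - Phi( ln(1.25) / (sqrt(2) x sigma) )

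- c = 10%: sigma = 0.0998, ratio 1.582, q = 5.7%
- c = 20%: sigma = 0.1980, ratio 0.797, q = 21.3%
- c = 30%: sigma = 0.2936, ratio 0.537, q = 29.5%

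Step 3. Expected number per 30 controls with HBsAg loss who fail ALT at that visit, 0.9q: 0.05, 0.19, 0.27.

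Step 4. Controls still on NUC have chemistry again at follow-up Weeks 36 and 48, and Section 6.8 can be met at either. Under the same model, with HBsAg loss persisting and one shared baseline deviation z, the probability of failing at Weeks 24, 36 and 48 is

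q3 = integral of phi(z) x [1 - Phi( (ln(1.25) + sigma z) / sigma )]^3 dz

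- q3 = 0.6%, 5.6%, 9.8%
- q3/q = 11%, 26%, 33%
- expected per 30, 0.9 x q3: 0.006, 0.05, 0.09

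So 67-89% of those failing at Week 24 would meet the ALT condition at a later visit within the study.

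**The case against.** The strongest reply is that the governing rule is easy to find. Section 6.8 is the section on stopping NUC, the Appendix 7 text cites it by number, and footnote n can be read as shorthand for that pathway. Sites do not routinely see HBsAg results (Protocol Section 6.4.1), so a site is unlikely to act on the footnote by itself. Anyone who does stop is followed every two weeks for 12 weeks and then monthly, with HBV DNA-triggered extra monitoring and explicit restart rules.

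Most of this stands as a limit on harm. It does not remove the conflict: the footnote is current, says that participants will stop, and cites nothing.

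Two further points stand as limits on what can be claimed:

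- A reader might infer from SAP item B that the plan foresees this situation in controls. It does not say so. Item B names neither the control arm nor the failed condition, and it could also cover people with HBsAg loss who left study drug early, to whom Section 6.8 does not apply. It shows only that HBsAg loss and meeting the stopping criteria are treated as different things.
- A reader might infer from the footnote that controls are meant to stop NUC in mid-treatment. The words permit that reading, but the marker's position at Week 48 makes a stop at or after Week 48 the likelier intention.

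**Conclusion.** The conflict is real and rests on the text alone; no figure is needed to establish it. It is an internal inconsistency of minor severity and does not call any design choice into question.

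The size is very small: 0.05-0.27 per 30 controls at one visit, and about 0.006-0.09 per 30 who would still not have met the ALT condition by follow-up Week 48. The usual difference is therefore an earlier stopping date. These figures rest on the 3% rate, the assumed 10-30% ALT CV, a stable ALT level and persistent HBsAg loss. They count the ALT condition only, because the documents give no basis for the frequency of HBV DNA or HBeAg failures. They also refer to the initial 30 controls; the control arm grows as arms are added, and the expected counts grow in proportion.

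A reader might turn the single-visit probability into a chance that at least one control is affected: 1 - (1 - 0.03q)^30 = 5.0%, 17.5% and 23.4%. That overstates the effect, because most of those counted would meet the ALT condition at a later visit. Nor do the documents support a claim that the primary result is compromised: the primary estimand uses observed HBsAg under a treatment-policy strategy, and neither it nor the planned analyses depend on footnote n.

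**What to change.** Replace footnote n of Appendix 7-Table 2 with: *NUC is discontinued only if the Section 6.8 criteria are met on samples taken at end-of-treatment or at a follow-up visit.* This aligns the schedule with Section 6.8 and the Appendix 7 text on population, timing and all four conditions. The cost is one line of protocol wording. No SAP change is needed.
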